In the event of a serious adverse event, and additionally, any non-serious events of malignancy in patients 30 years of age and younger, whether related to adalimumab or not, if applicable - the physician will notify the AbbVie contact person (Medical Representative in Japan) within 24 hours of the physician becoming aware of the event.

7. Duration of the investigation

Registration period: November 2011 ~ October 2013

Investigation period: November 2011 ~ March 2017

<Milestones>

Major study milestones and their planned dates are as follows:

Start of Data Collection: November 2011

Registration in the EU PAS register: Not Applicable

End of Study: The date on which statistical analysis dataset for

8. Items to be investigated

(1) Observation period

Patients will be observed for 3 years after the initiation of Humira treatment. (Patients who will continue Humira treatment for more than 3 years will also be evaluated at the end of third year to enable completion of the CRF). Patients who have been lost to follow-up during the observation period due to transfer to another hospital, discontinuation of treatment* or for other reasons will be handled as cases of discontinuation of the survey.

* A patient who has suspended Humira treatment for at least 2 months should be considered a case of discontinuation of Humira treatment that will be handled as a case of discontinuation of the survey.

(2) Registration form

Name of institution, date of completion of the registration form, name of department, name of investigator, patient ID, patient's birthdate (year/month) or age, sex, presence/absence of pregnancy/lactation (for female patients), reasons for use of Humira, date (or planned date) of initiation of Humira treatment, contraindications to use of Humira, conditions requiring special care in administration, presence/absence and effectiveness of previous treatment of Crohn's disease, history of biological therapy, presence/absence of tuberculosis or other infection (tuberculin skin test, Quantiferon test, chest X-ray, and chest CT), hepatitis B virus test (HBs antigen test), presence/absence of preventive anti-tuberculosis treatment, and baseline laboratory data (blood β-D-glucan level, peripheral blood WBC, and peripheral blood lymphocyte count).

(3) Data to be collected via CRF

1) Patient background

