2. Definitions of terms and abbreviations

The terms and abbreviations used in this analysis plan are as follows:

Term and abbreviation	Definition
Adverse event	Any untoward or unintended symptoms (including abnormal laboratory findings), condition or illness which are not always related to Humira.
Adverse events in the safety analysis period	Adverse events which occur from the first administration date of Humira through Week 160 of administration (Day 1 + 1120). Note that if a date is not provided, it should also be included in the period for analysis.
Adverse events not in the safety analysis period	Adverse events which occur prior to the first administration date of Humira or beyond Week 160 of administration (Day 1 + 1120).
Adverse reaction	Adverse events for which the causal relation with Humira cannot be ruled out.
Adverse reactions in the safety analysis period	Adverse events which occurred in the safety analysis period and for which the causal relation with Humira cannot be ruled out.
Adverse reactions not in the safety analysis period	Adverse events which occurred not in the safety analysis period and for which the causal relation with Humira cannot be ruled out.
MedDRA/J	Medical Dictionary for Regulatory Activities / Japanese edition
SOC	System Organ Class in MedDRA/J
PT	Preferred Terms in MedDRA/J
LLT	Lowest Level Terms in MedDRA/J
CDAI	Crohn's Disease Activity Index
WPAI	Work Productivity and Activity Impairment Questionnaire : Crohn's Disease
CRP	C-reactive protein
GB	Green book. Guide on re-examination

3. Objective of this statistical analysis plan

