	
record - 1 day for the final administration date.
 
Of note, if the final administration date is provided in the record where the final administration date of Humira has been identified according to the above rule and the “continued” checkbox is checked, follow the below:
 
 ● If the described final administration date > the final administration date imputed according to the above rule, select the imputed final administration date as the final administration date of Humira for the patient. ● If the described final administration date <= the final administration date imputed according to the above rule, select the described final administration date as the final administration date of Humira for the patient. 
If the first administration date of Humira + 1092 days < the final administration date of Humira imputed according to the above rule, select the first administration date of Humira + 1092 days as the final administration date of Humira.

Days to the final administration date of Humira	The final administration date of Humira - the first administration date of Humira + 1
Total exposure period (in years)	(Days to the final administration date of Humira + 28) / 364
Discontinued patients	
 • Patients whose final administration date of Humira comes before the first administration date of Humira + 1064 (Week 152) • Patients with a washout period with 60 days or longer. 
*The final administration date of Humira should be the administration date right before the washout of ≥ 60 days starts.

Reason for discontinuation	When a reason for discontinuation is described in the survey form, it is defined as ‘with’ reason for discontinuation. When no such description is found, it is defined as an “unknown/not provided”.
Death cases	At least a piece of data on “death” is found as the outcome of the adverse events during the safety analysis period.
Pediatrics	Patients aged < 15 years
The elderly	Patients aged ≥ 65 years

Data name	Derivation and calculation methods
Presence/absence of complications	When complication data are contained in the survey form, it should be classified as “with complications”. When the description in the survey form is not clear enough (when the check of with/without complications is not assessable or when multiple checkboxes are checked), it should be ‘unknown’ while no description should be ‘not provided’. Other cases are “no complications”.

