Note: When more than one identical PT is found in a patient, aggregate seriousness, days to the onset, outcome and days to the outcome (recovered or recovering) as 1 patient (case) in the following manner.

- Seriousness priority: serious > non-serious
- Days to the onset: identify the days as mentioned in “10.2 days from the first administration date of Humira to the adverse-event onset date”.
- Outcome: identify it as mentioned in “10.2 Outcome”.
- Days to outcome (recovered or recovering): identify the days as mentioned in 10.2 Days from an onset date of adverse events to the outcome confirmation date (recovered or recovering).

“2.4.2 A list of the onset status of the priority survey items per 100 patient-year”

Patients for analysis: patients in the safety analysis group

Analysis objective: to show the onset status of the priority survey items per 100 patient-year by adverse event, serious adverse event, adverse reaction, serious adverse reaction of patients in the safety analysis group.

Analysis items: calculate the number of patients and the percentage to the number of patients in the analysis groups per type of seriousness and type of priority survey items for adverse events/reactions which occurred between the first administration date of Humira and the final administration date of Humira + 28.

In addition, calculate the number of events/reactions and the event rate per 100 patient-year.

Note: Aggregate the total number of developed events/reactions including the overlapped ones which occurred in a patient.

“2.5.1 A list of the onset status of adverse reactions with/without self-administration”

Patients for analysis: patients in the safety analysis group

Analysis objective: to show the onset status of adverse reactions with/without self-administration

Analysis item: aggregate the following items with/without self-administration for adverse reactions which occurred in the safety analysis period.

Calculate the number of patients and the percentage to the number of patients surveyed per number of patients surveyed, number of patients with adverse reactions, etc. number of adverse reactions, type of adverse reactions, etc. (SOC, PT).

“2.5.2 A list of the onset status of adverse reactions with/without self-administration”

Patients for analysis: patients excluded from the safety analysis group

Analysis objective: to show the onset status of adverse reactions with/without self-administration

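### Person-time for the rate per 100 patient-years is not limited to time under observation, so chart 2.4.2 can understate the priority-event rates

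*SAP*

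**What the plan says.** SAP 10.1 counts treatment days as "The final administration date of Humira - the first administration date of Humira + 1" and defines total exposure in years as ("Days to the final administration date of Humira + 28) / 364". Where the imputed last dose falls later than the limit, the SAP says to "select the first administration date of Humira + 1092 days as the final administration date of Humira". The same section covers a final dosing record that is ticked as continued and has no end date: its last dose is set to first dose + 1092 days.

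For chart 2.4.2, SAP 13.2 takes "adverse events/reactions which occurred between the first administration date of Humira and the final administration date of Humira + 28" and asks the analyst to "calculate the number of events/reactions and the event rate per 100 patient-year". The chart text does not name the person-time variable. The 10.1 definition is the only one in the SAP, so its use here is an inference.

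The general safety analysis period in SAP section 2 is "Adverse events which occur from the first administration date of Humira through Week 160 of administration (Day 1 + 1120"), with the addition "Note that if a date is not provided, it should also be included in the period for analysis". Protocol 8(1) states "Patients will be observed for 3 years after the initiation of Humira treatment". Protocol 6(3) has the CRF completed without delay when treatment stops, and Protocol 8(1) treats transfer and loss to follow-up as discontinuation of the survey.

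**The concern.** A rate per patient-year is interpretable only if the denominator is time during which an event would have been recorded. The SAP builds the denominator from dosing dates alone. A patient who dies, moves hospital or stops attending keeps accruing time to last dose + 28 days. If the last available record says that treatment is continuing, time accrues to the end of Year 3. Unobserved time enlarges the denominator and adds no events, so any error lowers the rate.

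Two smaller features act the same way or may do so. A 364-day year is used for a figure labelled patient-years. The event count is tied to a dated interval, and the chart does not say what happens to events without a date.

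Chart 2.4.2 is the only exposure-adjusted result for the survey's priority items, and a low rate is the favourable direction in a safety survey.

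**Working it through.** The documents state no rate and no total person-time. The SAP figure that can be reproduced is the Week 160 limit.

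1. **Limit.** 1092 + 28 = 1120 = 160 × 7. Exposure therefore ends no later than the safety analysis period in SAP section 2.

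2. **Do numerator and denominator cover the same days?** Let F be the first dose and L the last. Denominator days are (L − F + 1) + 28. The chart 2.4.2 window, counted inclusively, is (L + 28) − F + 1. These are equal for every L, with a maximum of 1092 + 1 + 28 = 1121 days. With full capture of events, the 28 days cause no bias.

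3. **Patients lost while recorded as continuing.** A patient last seen at day 365 whose final record is ticked as continued gets L = F + 1092, so 1121 days are credited and 1121 − 365 = 756 are unobserved. Because L is not before F + 1064, the patient is not classed as discontinued on that criterion either.
   - Assume 25 such patients: 25 × 756 = 18,900 days.
   - For the total, assume 500 patients of whom 40% stop evenly over three years. Mean treated time is 0.6 × 1093 + 0.4 × 547 ≈ 875 days. Adding 28 gives 903, and 500 × 903 = 451,500 days.
   - 18,900 / 451,500 = 4.2%, or 18,900 / 470,400 = 4.0% if those days come on top. The share scales with the number of patients: 5 give 0.8% (3,780 / 451,500) and 50 give 8.4% (37,800 / 451,500).

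4. **The 28-day tail, if no event in it is captured.** The understatement is 28 / (d + 28) for d treated days: 2.5% at 1093, 7.1% at 365 and 13.3% at 183. These are upper bounds. They concern mainly early stoppers whose CRF is completed at once.

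5. **Death.** With k deaths on the last dosing day, the excess share is 28k / total days. For an assumed 1 to 10 deaths among 500 and mean treatment of 365 to 1093 days, it runs from 28 / (500 × 1121) = 0.005% to 280 / (500 × 393) = 0.14%.

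6. **Year length.** 364 / 365.25 = 0.9966, so every rate is 0.34% too low. For an assumed 3 events in 300 completers, the rate is 0.3247 per 100 patient-years with 364 and 0.3258 with 365.25.

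7. **Undated events.** SAP 9.1 sets a date with only a year, or with nothing known, to null. SAP 10.2 computes days to onset only from complete dates. A null date cannot be placed between two dates, and the keep-undated rule in section 2 belongs to a different period. The same event could therefore count in chart 2.4.1.2 and be missing from 2.4.2. For scale, assume 500 patients treated 729 days on average. Person-time is 500 × 757 / 364 = 1,039.8 years. Five dated events give 0.481 per 100 patient-years, and counting a sixth, undated event gives 0.577.

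**The case against.** A reader might infer that the formula is biased low by construction, with 28 days added to every denominator and no limit at the end of observation. The documents do not support that. Chart 2.4.2 extends its event window by the same 28 days, and the 1092-day limit holds exposure to Week 160. A figure of about 3.4%, combining the tail and the 364-day year, would need zero capture in every patient's tail. It would also need the 500-to-300 planning margin to be a real attrition estimate.

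Nor is the tail a period without data collection:
- SAP 12.1 accepts Year 3 assessments on Days 1065 to 1121.
- SAP 12.4 has an onset period from Day 1093.
- SAP 10.2 adds events from detailed investigations outside the survey form.
- Protocol 6(4) requires serious events to be notified within 24 hours.
- Where discontinuation follows a suspension of two months or more, that gap already covers 28 days.

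The 364-day year is also the SAP's consistent calendar (1092 = 3 × 364), and 0.34% is trivial beside sampling error: with 3 events, the exact 95% Poisson limits are 0.62 to 8.77 events. It would also go too far to say that undated events are excluded, because the chart is silent and the SAP's one explicit rule keeps them.

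All of this stands. It does not answer the missing end of person-time at last contact. The Week 160 limit is the end of the analysis period, not of an individual patient's observation. The tail also runs about 25 days past the protocol's three years (1120 against 1095 to 1096 days), and a CRF completed at discontinuation does not assure capture of later events.

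**Conclusion.** The point holds as a minor one: the rate in chart 2.4.2 can be understated because person-time is not tied to observation. The clearest route is the imputation to first dose + 1092 for patients lost while recorded as continuing. It amounts to about 4% if 25 of 500 patients are affected at day 365, and both numbers are assumptions. Ending person-time at death alone changes 0.14% or less under the assumed ranges. The 364-day divisor costs a certain but small 0.34%. The 28-day tail matters only where events after the last dose go unreported.

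The undated-event gap could move a rate based on few malignancies more than any of these, but the number of such events is unknown and may be zero. The conclusion also rests on the inference that chart 2.4.2 uses the exposure variable in SAP 10.1.

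**What to change.** In SAP 10.1, define person-time as first dose to the earliest of last dose + 28 days, death, and last date with safety information, with first dose + 1120 days as the limit for all patients. Patients still on drug should keep the same 28-day tail as those who stopped. Define the last date with safety information explicitly, for example from the last locked CRF or the last reported event, since the SAP has no such variable. Divide by 365.25.

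In chart 2.4.2, cite this variable by name and count events over exactly the same interval. Include events with missing or partial onset dates unless the known parts of the date place them outside it.

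The cost is a few lines of SAP text, one more derived variable and slightly less favourable rates.

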9.4. Figure display rule

Case	Display rules
If a figure is incalculable	Hyphen “-”

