10.1. General

Data name	Derivation and calculation methods
Number of sites for this survey	Aggregate the number with DCF code.
The first administration date of Humira	It shall be the oldest date among the dates described in “the administration status of Humira” in the survey form.
The final administration date of Humira	
Do not use for analysis the record of the first administration date of Humira + 1092 days < the first administration date among the data described in “the administration status of Humira” in the survey form.
 
The final administration date of Humira shall be the most recent date among the final administration dates imputed in the following [1] to [4]:
 
[1] Sort data in the order of “the first administration date” of “the administration status of Humira”, dosing frequency and description.
 
[2] If the final date is provided, there is no check on the checkbox of “continued”, and the final administration date can be identified, select the date described as the final administration date.
 
If the final date is not described, the checkbox of “continued” is checked, and the final administration date cannot be identified, follow the below:
 
 • The final record: Impute the first administration date of Humira + 1092 days on the final administration date. • Other than the final record: Impute the first administration date of the next record - 1 day on the final administration date. 
[3] Even though the final dates are described, but the final administration date is incomplete and cannot be identified, follow the below:
 
 • If the year and month are described but the date is unknown, impute the final date of the month as the final administration date. • If the year is described and the month and date are unknown, impute the final date of the year as the final administration date. If the next record has already been generated and the first administration date of the next record comes earlier than the imputed date, impute the first administration date of the next

Data name	Derivation and calculation methods

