	
If all the following [1] to [4] are satisfied, aggregate the data as “160mg \rightarrow 80mg \rightarrow 40mg once every two weeks”. Others are aggregated as “others”.
 
Of note, when data on administration status include only [1], [2] and [3] or when the data ends halfway for some reason, determine whether the case satisfies the criteria from [1] to [4] as of the final data on administration status, and classify it.

Data name	Derivation and calculation methods
Administration status (total number of dosing, total dose)	
 Dosing frequency 
[1] Sort data in the order of “the first administration date” of “the administration status of Humira”, dosing frequency and description.
 
[2] Calculate the dosing interval per data on administration status. “When “once every two weeks” is checked, regard it as a 14-day interval. For others, obtain the frequency from “dosing interval”.
 
[3] Calculate the dosing frequency per data on administration status. Dosing frequency = (the final administration date (the date imputed based on the definition of 10.1 Final administration date of Humira) – the first administration date(after imputed))/dosing frequency (number of days)
 
When the results of [4] and [3] are “>0” (bigger than 0) and “<1” (smaller than 1), count it as 1.
 
If the figure is “>=1” (1 or bigger), round the decimal down to the integer for the dosing frequency.
 
[5] The total number of dosing shall be the total of [4] per patient.
 Dose 
[1] When the dose of Humira is ‘others’, obtain the dose from “Dose_other description”.
 
[2] Calculate the dose per data of the administration status.
 
Dose = the number of dosing * a dose
 
[3] The total dose should be the total of [2] per patient.
 The mean of a dose 
The mean of a dose = the total dose/the total number of dosing

Patients with self-administration	The patients whose registration form has a check on self-administration.
Age	It should be identified based on the date of birth or the first administration date of Humira in the survey form. Of note, if the “date” of birth is incomplete and not provided, impute 1 as the date. When the date of birth is still incomplete even after the above imputation, just mirror the age provided in the survey form.

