10.3. Effectiveness analysis

Data name	Derivation and calculation methods	
Remission	When the CDAI score is <150, the case is regarded as remission.	
WPAI	
Q1 Do you work now? Yes, no
 
Q2 How many hours did you leave the work due to problems related to Crohn's disease over the past 7 days? () hour(s)
 
Q3 How many hours did you leave the work for a reason other than Crohn's disease such as holidays or hours for which you were off to participate in this survey over the past 7 days? () hour(s)
 
Q4 How many hours did you actually work for the past 7 days? () hour(s)
 
Q5 How much productivity was affected by Crohn's disease while you were working over the past 7 days? 0: Crohn's disease did not affect the work. 10: Crohn's disease completely interrupted the work. Based on the above, your score between 0 to 10. ()
 
Q6 How much did Crohn's disease affect various daily activities except your job over the past 7 days? ()
	

Data name	Derivation and calculation methods		
		
0: Crohn's disease did not affect daily activities.
 
10: Crohn's disease completely interrupted daily activities.
 
Based on the above, your score between 0 to 10.
	

- Absenteeism (%)

Calculate it with the following formula based on the questions (Q1 to Q6) on the above table:

$$[Q2 / (Q2 + Q4)] \times 100$$

- Presenteeism (%)

Calculate it with the following formula based on the questions (Q1 to Q6) on the above table:

$$(Q5 / 10) \times 100$$

- Overall work impairment (%)

Calculate it with the following formula based on the questions (Q1 to Q6) on the above table:

$$\{ Q2 / (Q2 + Q4) + [1 - Q2 / (Q2 + Q4)] \times (Q5 / 10) \} \times 100$$

- Activity Impairment (%)

Calculate it with the following formula based on the questions (Q1 to Q6) on the above table:

$$(Q6 / 10) \times 100$$

11. How to stratify data

Data	How to stratify
Dosage and administration	160mg→80mg→40mg once every two weeks, other
Dosing frequency (times)	≥1 and <4, ≥4 and <13, ≥13 and <26, ≥26 and <39, ≥39 and <52, ≥52 and <65, ≥65 and <78, ≥78
Total dose (mg)	<500mg, ≥500mg and <1000mg ≥1000mg and <2000mg ≥2000mg and <3000mg ≥3000mg, Unknown

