Number of described complications: the number of PT codes encoded by MedDRA/J. If more than 1 identical PT code is found in a patient, count the PT as 1. Describe “0” for the case with no complications.

Term: Describe the PT of complication encoded by MedDRA/J. Arrange detailed classification of complication, the name of complication disease name, a serial number of the complication per patient. Leave the column blank for the case with no descriptions.

(12) Route of administration

Describe it as “SC”.

(13) Maximal dose (a dose)

The maximum of a dose Select the largest number in “administration status defined in “10.1 General” per patient.

(14) The mean dose (a dose)

The mean of a dose

It should be the value of “total dose/total dosing times” based on the “administration status (total dosing time, total dose)” defined in “10.1 General”.

(15) Unit

Use “MG”.

(16) daily dosing frequency (the maximum)

Use “1”.

(17) Period for administration

The value of “total dosing time” based on “ administration status (total dosing time, total dose)” defined in “10.1 General”.

(18) Concomitant medications

Drug code, the principal drug name: arrange concomitant medications for Crohn's disease (the concomitant medications checked at the indication: Crohn's disease in the survey form) per patient in the order of separate volume and description, and choose the concomitant medication data at the top. If there is no concomitant medication, leave the drug code column blank, and the name of the primary drug “null”.

Number of descriptions: count the number of the drug codes for concomitant medications arranged with the rule mentioned above. If more than 1 identical drug code is found in a patient, count it as 1 (for all the concomitant medications no matter whether the indication: Crohn's disease is checked). Describe “0” for the case with no concomitant medications.

(19) Effectiveness level

Follow Time Allowance of “12.1 Assessment period for CDAI, WPAI, CRP and no-intestinal conditions” to display remission/non-remission at the final assessment. Of note, if remission/non-remission at the final assessment is not reported, regard it as “unknown”.

(20) Adverse reactions

Handle the events with the identical PT code in a patient as 1 record regarding adverse events which occurred in the safety analysis period.

Organ-name code: select the SOC code. When presence/absence is “absence”, leave the column blank.

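### The SAP's dose-count rule counts intervals between injections, not injections, so most records come out one dose short and a same-day record counts as zero

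*SAP*

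**What the plan says.** SAP 10.1 (General), in the entry for total number of doses and total dose, works record by record. It subtracts the first date from the final date and divides by the interval in days ("the first administration date(after imputed))/dosing frequency (number of days"). Once every two weeks is taken as 14 days. A result above 0 and below 1 is set to 1. For a result of 1 or more the instruction is to "round the decimal down to the integer for the dosing frequency". No branch covers a result of exactly 0. Record counts are summed per patient, multiplied by the single dose to give total dose, and used as the divisor of the mean dose.

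The dates come from the final-administration-date entry in the same section:

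- An identified final date is used as recorded.
- A record marked as continuing, with no final date, is handled thus: "Other than the final record: Impute the first administration date of the next record - 1 day on the final administration date".
- If only year and month are known, the rule is to "impute the final date of the month as the final administration date"; if only the year is known, year-end is used.

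For days on treatment, 10.1 counts inclusively: "The final administration date of Humira - the first administration date of Humira + 1". The dose-count strata in SAP 11 begin "≥1 and <4, ≥4 and <13, ≥13 and <26".

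**The concern.** If the two dates are those of the first and last injection in a record, the difference divided by the interval is the number of gaps between injections, which is one fewer than the injections. The same section adds 1 when it counts days but not when it counts doses. The branch that raises fractional results to 1 suggests that every treated record was meant to contribute at least one dose, yet a record with equal dates evaluates to 0.

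The counts feed chart 1.6.1 (distribution of number of doses and total dose) and two items of Attachment Form 3 (chart 2.3): item 14, mean dose ("It should be the value of “total dose/total dosing times” based on"), and item 17, period of administration. SAP 3.1 says the plan serves the regulatory report and the re-examination application, so misstated exposure would be carried into both.

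**Working it through.** The plan states no numerical result for this rule, so there is none to reproduce.

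**Rule as written.** r = (final − first)/interval. Count = 1 if 0 < r < 1; floor(r) if r ≥ 1; the formula's value, 0, if r = 0.

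**True count.** With known, on-schedule dates: floor(r) + 1.

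**Single records, 14-day interval**

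| Days | r | SAP count | True |
|---|---|---|---|
| 1–1 | 0/14 = 0 | 0 | 1 |
| 1–14 | 13/14 | 1 | 1 |
| 1–15 | 14/14 = 1 | 1 | 2 |
| 29–43 | 14/14 = 1 | 1 | 2 |

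The rule is one too low whenever r is 0 or at least 1, and right in between. Intervals of 7, 21 and 28 days show the same shortfall. It also holds when the final date falls up to 13 days after the last of two or more injections.

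**SAP's own imputed end date.** If a record of k on-schedule doses ends the day before the next record starts, r = (14k − 1)/14. For k = 1 this is 13/14, counted correctly as 1. For every k ≥ 2 it rounds down to k − 1.

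**A patient with one equal-date record.** The count is 0 and the dose 0 mg. The count falls below the lowest stratum, and the mean dose is 0/0, shown as a hyphen under SAP 9.4 ("If a figure is incalculable").

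**Three-year patient** on the 160/80/40 mg two-weekly pattern that SAP 10.1 uses for classification. Injections on Days 1, 15, …, 1093 number 1092/14 + 1 = 79. The dose is 160 + 80 + 77 × 40 = 3320 mg and the mean 42.03 mg. The survey form is not shown, so the layouts are assumptions:

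| Layout | Records (days) | SAP count | SAP dose (mg) | Mean (mg) |
|---|---|---|---|---|
| A | 1–14, 15–28, 29–1093 | 1 + 1 + 76 = 78 | 160 + 80 + 76 × 40 = 3280 | 42.05 |
| B | as A, but maintenance 29–182, 183–364, 365–546, 547–728, 729–910, 911–1093 | 1 + 1 + 10 + 4 × 12 + 13 = 73 | 160 + 80 + 71 × 40 = 3080 | 42.19 |
| C | 1–1, 15–15, 29–1093 | 0 + 0 + 76 = 76 | 76 × 40 = 3040 | 40.00 |
| D | 1–1, 15–15, maintenance as B | 0 + 0 + 71 = 71 | 71 × 40 = 2840 | 40.00 |

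B, C and D drop out of the ≥78 dose stratum; only D drops below 3000 mg. Under A, patients whose true count is 4, 13, 26, 39, 52, 65 or 78 fall one stratum too low, because those are the cut-points.

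**Late imputed end date.** Five injections on Days 29–85: the rule gives 4 if the imputed end is 0–13 days late, 5 if 14–27 and 6 if 28–30. The shortfall can therefore vanish or reverse.

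**The case against.** The strongest counter-argument is that the end-date field may mark the end of a covered period. From the third administration the protocol (8(3)4)) collects interval and duration, not individual injections. If sites enter the last dose plus a full interval, or the next record's start date, the rule counts that record correctly. This is a real condition on the finding. However, the SAP calls the field the final administration date, uses identified dates as recorded, and nowhere defines it as a period end. Its own day-before-next-record imputation still loses a dose for every record of two or more.

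Second, 79 depends on an injection on Day 1093. SAP 12.3 ends Year 3 at Day 1092, and Days 1–1092 hold 1092/14 = 78 scheduled injections, so layout A would then be right. SAP 10.1 does allow a final administration date of first date + 1092, which is Day 1093. For a continuing final record that date is imputed, and the shortfall there exists only if an injection that day is counted. Against 78, layouts B, C and D are still 5, 2 and 7 short.

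Third, C and D need equal start and end dates on the loading records. The protocol lists only a date for the first and second administrations, which makes this plausible but not shown. If the end date is blank and filled from the next record, layout A applies. Likewise, the 0 for equal dates is the formula's value; the SAP does not state it.

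Fourth, adding 1 does not help every imputed date. In the late-end example it gives 5, 6 and 7 where the SAP gives 4, 5 and 6, so it can be two too high. This stands, and it is why such records need flagging.

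**Conclusion.** The rule is wrong as written. Read literally, with known on-schedule dates, it is one dose short for every record whose result is 0 or at least 1, and the shortfall accumulates over a patient's records. For a three-year patient it ranges from 1 dose and 40 mg (layout A, 1.2% of dose) to 8 doses and 480 mg (layout D), depending on a form that is not shown. A same-day record loses its dose entirely.

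The direction is not uniform once end dates are imputed to month-end or year-end. The consequence is confined to descriptive exposure: number of doses, total dose and mean dose. Patient-year rates rest on days of administration, and neither the incidences nor the background-factor tests use the dose count. The correction should be made because it is cheap and the figures go into a regulatory form; it does not threaten the safety or effectiveness conclusions.

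**What to change.** In SAP 10.1, replace steps [3] and [4] by: doses per record = floor((final date − first date)/interval) + 1, applied to every record including those with equal dates.

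Add a guard: where a record's final date equals the next record's first date, end the earlier record one day before, so that the injection is counted once. With maintenance records sharing boundaries (29–183, 183–365, …, 911–1093, loading as in A), the present rule gives 78 doses and 3280 mg. Adding 1 without the guard gives 84 and 3520 mg; with the guard, 79 and 3320 mg. The guarded rule also returns 79 and 3320 mg in layouts A to D.

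Flag records whose end date was imputed to month-end or year-end, and give the number of such patients in a footnote to chart 1.6.1, since their counts are approximate under either rule. The SAP should also say which interval value the program uses for first- and second-administration records, because the protocol lists an interval only from the third; the calculations above take 14 days.

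The cost is one formula, one date check and one flag in the SAP and program. No new data are needed.
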